5.5 Drug Supplies

5.5.1 Formulation and Packaging

The MGL-3196 active drug substance, 2-[3,5-Dichloro-4-95-isopropyl-6-oxo-1,6-dihydro-pyridazin-3-yloxy)-phenyl]-3,5-dioxo-2,3,4,5-tetrahydro-1,2,4]triazine-6-carbonitrile, is a white to tan crystalline powder stable for 60 months at 25°C/60% relative humidity and 6 months at 40°C/75% relative humidity.

MGL-3196 capsules consist of MGL-3196 active ingredient, pregelatinized starch (Starch 1500), colloidal silicon dioxide (Cab-O-Sil), and magnesium stearate encapsulated in #2 Swedish-orange hard gelatin capsules. MGL-3196 capsules are made in accordance with ICH and FDA guidelines.

MGL-3196 capsules are packaged in high-density polyethylene plastic bottles with child-resistant closures. MGL-3196 and matching placebo are available as hard gelatin capsules for oral administration in 40 mg and 60 mg strengths. Product labels will be identical except for a unique identifying code. Patients will receive 2 bottles with the additional labels of A and B. Each bottle will contain 32 capsules (64 capsules total).

5.5.2 Study Drug Preparation and Dispensing

Study drug will be bottled and labeled by [REDACTED] using current Good Manufacturing Practice. Study drug will be assigned by Interactive Response Technology (IRT) to study site/patients.

5.5.3 Study Drug Administration

Study drug will be administered in the morning at the Week 1, 4, 8, and 12 study visits. Each patient will receive 2 bottles labeled as A and B. The patient will take 1 capsule from bottle A and 1 capsule from bottle B at each dosing. Each bottle will contain 32 capsules (64 capsules total), enough for 4 weeks + 4 days.

5.5.4 Treatment Compliance

Patients will be assessed for study drug compliance at each visit. On Day 1, patients will receive a study drug journal in which to record study drug compliance. Site staff will record the number of capsules taken from each study drug bottle and record this information in the patient's eCRF. If at any visit the patient is <80% compliant, the patient will be counseled on the importance of compliance to the study regimen. If at the end of study, the patient is <80% compliant over the course of the 12-week Treatment Period, the patient will not be included in the Per Protocol Population.

5.5.5 Storage and Accountability

Adequate records on receipt, use, return, loss, or other disposition of medication must be maintained. Other required data includes relevant dates, quantities, unique bottle code, and patient identification for patients who receive study drug. Patients will be instructed to return all unused study medication to the Investigator, in the original bottles. At the end of the study, all unused products will be collected and destroyed according to institutional pharmacy policies and procedures. The study drug will be stored according to manufacturing guidelines (see Section 5.5.1).

5.6 Prior and Concomitant Medications and/or Procedures

5.6.1 Excluded Medications and/or Procedures

Excluded medications and/or procedures include:

- Major inhibitors of OATP transporters such as gemfibrozil, cyclosporine A, or protease inhibitors;
- Repaglinide or a glitazone such as rosiglitazone (substrates of CYP2C8) or gemfibrozil (inhibitor of CYP2C8);
- Glipizide or tolbutamide treatment;
- Warfarin treatment;
- Fibrates, PCSK9 inhibitors (within 4 months prior to randomization), or niacin;
- Prior or planned (during the study period) upper gastrointestinal surgery, including bariatric surgery (eg, gastroplasty, roux-en-Y gastric bypass);
- GLP-1 analogue or complex oral antidiabetic regimen (3 or more oral antidiabetic drugs). Patients are allowed to be on insulin if there has been no change $>10\%$ in unit dose in the 2 months prior to screening, and they are allowed to be on up to 2 oral antidiabetic drugs; and
- Systemic steroids, herbal supplements (eg, kelp), or iodine supplements that can affect thyroid or weight loss medications.

5.6.2 Documentation of Prior and Concomitant Medication Use

All concomitant medications must be recorded in the eCRF. Any prior medication received within 30 days of the first dose of study drug will be recorded in the eCRF. Concomitant treatments that are required to manage a patient's medical condition during the trial will also be recorded in the eCRF.

Patients taking bile acid sequestrants should take them approximately 4-6 hours after taking their MGL-3196 study drug or matching placebo and approximately 4-6 hours prior to their evening statin dose.

6 STUDY PROCEDURES

6.1 Informed Consent

Informed consent will be obtained at the Screening Visit (Day -14 to Day -1) prior to performing any study-related procedures.

6.2 Screening Visit (Day -14 to Day -1)

The following procedures will be performed at the Screening Visit:

- Obtain informed consent;
- Collect demographic information and review medical history;
- Assess eligibility;
- Collect vital signs;
- Measure height and weight (calculate body mass index);
- Perform 12-lead ECG;
- Perform complete physical examination;
- Collect blood samples for the following assessments:
 - Hematology and chemistry;
 - Serum pregnancy test (female patients only);
 - Coagulation panel;
 - Thyroid function test (except TBG);
 - Lipid panel, apolipoproteins, and lipoprotein(a);
 - [REDACTED]
 - HbA1c;
 - Hepatitis panel, including hepatitis B, HBsAg, HCV, and HCV antibody (HCVAb); and
 - HIV;
- Collect urine sample for the following assessments:
 - Urinalysis, and
 - Urine drug screen;
- Provide diet and lifestyle counseling; and
- Review concomitant medications.
- Verify on stable maximally tolerated dose of atorvastatin or rosuvastatin (up to 20 mg) and adjust statin dosing to once daily in evenings

6.3 Randomization

Patients will be randomized at the Baseline Visit (Day 1).

6.4 Treatment Period – Day 1 Through Day 84

Following randomization to study medication at the Baseline Visit, patients will return for visits and procedures to occur within ± 3 days of the scheduled date. In all cases, the patient should arrive at the clinic in the morning after at least 10 hours of fasting, and record the time they took their statin the night before.

6.4.1 Baseline Visit (Day 1)

The following procedures will be performed at the Baseline Visit:

- Assess eligibility;
- Randomize patients;
- Collect vital signs;
- Measure weight;
- Perform 12-lead ECG;
- Perform targeted, symptom-directed physical examination;
- Collect blood samples for the following assessments:
 - Hematology and chemistry;
 - Coagulation panel (prothrombin time [PT] and activated partial thromboplastin time [aPTT] only);
 - Thyroid function test;
 - Lipid panel, apolipoproteins, ApoCIII, and lipoprotein(a);
 - Lipoprotein particle analysis;
 - LDL-C by ultracentrifugation;
 - FSH, total and free (calculated) testosterone, LH, CKMB, troponin I, reverse T3, ALP isoenzymes, P1NP, CTX, and fibrinogen. Free testosterone will be calculated from total testosterone, [REDACTED], and serum albumin;
 - [REDACTED];
 - HbA1c;
 - Genomics;
 - Backup sample;
 - [REDACTED]
 - [REDACTED]; and
 - Pre-dose PK (measurement of statin level);

- Collect urine sample for the following assessments:
 - Urinalysis, and
 - Human chorionic gonadotropin (if applicable);
- Assign study drug via IRT;
- Dispense study drug for Weeks 1-2; and
- Review concomitant medications and adverse events.

6.4.2 Week 2 (Day 14 [± 3 days])

Patient arrives at the clinic in the morning fasting. The following procedures will be performed at Week 2:

- Collect vital signs;
- Measure height and weight (calculate body mass index);
- Perform targeted, symptom-directed physical examination;
- Collect blood samples for the following assessments:
 - Hematology and chemistry;
 - Serum pregnancy test (female patients only);
 - Thyroid function test;
 - Lipid panel, apolipoproteins, ApoCIII, and lipoprotein(a);
 - [REDACTED]; and
 - Pre-dose and 4-hr post dose PK (for statins and MGL-3196);
- Perform 12-lead ECG at 4 hours post dose (after second blood draw);
- Assess study drug accountability;
- Dispense study drug for weeks 3-4 via IRT;
- Review concomitant medications and adverse events; and
- Verify on statin dose and once daily in evenings.

6.4.3 Week 4 (Day 28 [± 3 days])

Patients will arrive at the clinic fasting. The following procedures will be performed at Week 4:

- Collect vital signs;
- Measure height and weight (calculate body mass index);
- Perform targeted, symptom-directed physical examination;
- Collect blood samples for the following assessments:
 - Hematology and chemistry;

- Serum pregnancy test (female patients only);
- Thyroid function test;
- Lipid panel, apolipoproteins, ApoCIII, and lipoprotein(a);
- [REDACTED] and
- Pre-dose PK;
- Perform 12-lead ECG (after 30 minutes of rest following blood draws);
- Assess study drug accountability;
- Dispense study drug for weeks 5-8 via IRT; and
- Review concomitant medications and adverse events.

6.4.4 Week 8 (Day 56 [± 3 days])

The following procedures will be performed at Week 8:

- Collect vital signs;
- Measure height and weight (calculate body mass index);
- Perform 12-lead ECG;
- Perform targeted, symptom-directed physical examination;
- Collect blood samples for the following assessments:
 - Hematology and chemistry;
 - Serum pregnancy test (female patients only);
 - Thyroid function test;
 - Lipid panel, apolipoproteins, ApoCIII, and lipoprotein(a);
 - [REDACTED];
 - HbA1C; and
 - Pre-dose PK;
- Assess study drug accountability;
- Dispense study drug for weeks 9-12 via IRT; and
- Review concomitant medications and adverse events.

6.4.5 Week 12 (Day 84 [± 3 days]) or Early Termination Visit

The following procedures will be performed at Week 12 or at the Early Termination Visit:

- Collect vital signs;
- Measure weight;
- Perform 12-lead ECG;

- Perform targeted, symptom-directed physical examination;
- Collect blood samples for the following assessments:
 - Hematology and chemistry;
 - Serum pregnancy test (female patients only);
 - Coagulation panel;
 - Thyroid function test;
 - Lipid panel, apolipoproteins, ApoCIII, and lipoprotein(a);
 - Lipoprotein particle analysis;
 - LDL-C by ultracentrifugation;
 - [REDACTED];
 - FSH, total and free (calculated) testosterone, LH, CKMB, troponin I, reverse T3, ALP isoenzymes, P1NP, CTX, and fibrinogen. Free testosterone will be calculated from total testosterone, [REDACTED], and serum albumin;
 - HbA1c;
 - Backup sample;
 - [REDACTED]
 - [REDACTED]; and
 - Pre-dose PK;
- Collect urine sample for urinalysis;
- Assess study drug accountability; and
- Review concomitant medications and adverse events.

6.5 Follow-Up Visit at Week 16 (Day 112 [± 3 days])

The following procedures will be performed at the Follow-Up Visit at Week 16:

- Collect vital signs;
- Measure weight;
- Perform 12-lead ECG;
- Perform targeted, symptom-directed physical examination;
- Collect blood samples for the following assessments:
 - Hematology and chemistry;
 - Serum pregnancy test (female patients only);
 - Thyroid function test;
 - Lipid panel, apolipoproteins, ApoCIII, and lipoprotein(a);

- Lipoprotein particle analysis;
- [REDACTED]; and
- FSH, total and free (calculated) testosterone, LH, CKMB, troponin I, reverse T3, ALP isoenzymes, P1NP, CTX, and fibrinogen. Free testosterone will be calculated from total testosterone, [REDACTED], and serum albumin; and
- Review concomitant medications and adverse events.

6.6 Early Termination Visit and Withdrawal Procedures

For patients who are withdrawn from the study prior to completion, the procedures described for the Week 12 Visit (Section 6.4.5) will be performed at an Early Termination Visit.

7 EFFICACY ASSESSMENTS

The primary efficacy parameter is mean percent change from baseline in LDL-C.

The secondary efficacy parameters include the following:

- Mean percent change from baseline in non-HDL-C, ApoB, TC/HDL-C ratio, triglycerides, lipoprotein(a), ApoA1/ApoB ratio, and lipoprotein particle assessment; and
- Absolute percent change from baseline in LDL-C.
- Mean percent change from baseline in LDL-C for all patients on study drug (60-100 mg)
- Mean per cent change from baseline in LDL-C according to MGL-3196 exposure

The exploratory efficacy parameters include the following:

- [REDACTED]
- [REDACTED]
- [REDACTED]

8 PHARMACOKINETIC ASSESSMENTS

Blood samples for PK assessments will be obtained fasting pre-dose from patients at the Baseline Visit (Day 1), Weeks 2, 4, 8, and 12, and the Early Termination Visit. Blood samples for PK assessment will also be obtained 4 hours post-dose from patients at Week 2 under fasting conditions. Statin PK will also be assessed at baseline and Week 2 visits and may be assessed at later visits.

9 SAFETY ASSESSMENTS

9.1 Adverse Events

An adverse event is defined as any untoward medical occurrence in a clinical investigation patient administered a pharmaceutical product, which does not necessarily have a causal relationship with this treatment. An adverse event can therefore be any unfavorable and/or unintended sign (including an abnormal laboratory finding), symptom, or disease temporally associated with the use of an investigational medicinal product, whether or not related to the investigational medicinal product. All adverse events, including observed or volunteered problems, complaints, or symptoms, are to be recorded on the appropriate eCRF.

Adverse events, which include clinical laboratory test variables, will be monitored and documented from the time of informed consent until study participation is complete. Patients should be instructed to report any adverse event that they experience to the Investigator. Beginning at the Screening Visit, Investigators should make an assessment for adverse events at each visit and record the event on the appropriate adverse event eCRF.

Wherever possible, a specific disease or syndrome rather than individual associated signs and symptoms should be identified by the Investigator and recorded on the eCRF. However, if an observed or reported sign or symptom is not considered a component of a specific disease or syndrome by the Investigator, it should be recorded as a separate adverse event on the eCRF. Additionally, the condition that led to a medical or surgical procedure (eg, surgery, endoscopy, tooth extraction, or transfusion) should be recorded as an adverse event, not the procedure.

Any medical condition already present at screening should not be reported as an adverse event unless the medical condition or signs or symptoms present at baseline change in severity or seriousness at any time during the study. In this case, it should be reported as an adverse event.

Clinically significant abnormal laboratory or other examination (eg, ECG) findings that are detected during the study or are present at screening and significantly worsen during the study should be reported as adverse events. The Investigator will exercise his or her medical and scientific judgment in deciding whether an abnormal laboratory finding or other abnormal assessment is clinically significant. Clinically significant abnormal laboratory values occurring during the clinical study will be followed until repeat tests return to normal, stabilize, or are no longer clinically significant. Any abnormal test that is determined to be an error does not require reporting as an adverse event.

9.1.1 Adverse (Drug) Reaction

All noxious and unintended responses to a medicinal product related to any dose should be considered an adverse drug reaction. “Responses” to a medicinal product means that a causal relationship between a medicinal product and an adverse event is at least a reasonable possibility, ie, the relationship cannot be ruled out.

9.1.2 Unexpected Adverse Drug Reaction

An Unexpected Adverse Drug Reaction is defined as an adverse reaction, the nature or severity of which is not consistent with the applicable product information.

9.1.3 Assessment of Adverse Events by the Investigator

The Investigator will assess the severity (intensity) of each adverse event as mild, moderate, or severe, and will also categorize each adverse event as to its potential relationship to study drug using the categories of yes/no.

Assessment of Severity:

Mild – An event that is easily tolerated and generally not interfering with normal daily activities.

Moderate – An event that is sufficiently discomforting to interfere with normal daily activities.

Severe – An event that is incapacitating with inability to work or perform normal daily activities.

Causality Assessment:

The relationship of an adverse event to the administration of the study drug is to be assessed according to the following definitions:

No (unrelated, not related, no relation) – The time course between the administration of study drug and the occurrence or worsening of the adverse event rules out a causal relationship and another cause (concomitant drugs, therapies, complications, etc.) is suspected.

Yes (related) – The time course between the administration of study drug and the occurrence or worsening of the adverse event is consistent with a causal relationship and no other cause (concomitant drugs, therapies, complications, etc.) can be identified.

The definition implies a reasonable possibility of a causal relationship between the event and the study drug. This means that there are facts (evidence) or arguments to suggest a causal relationship.

The following factors should also be considered:

- The temporal sequence from study drug administration-
 - The event should occur after the study drug is given. The length of time from study drug exposure to event should be evaluated in the clinical context of the event.
- Underlying, concomitant, intercurrent diseases-
 - Each report should be evaluated in the context of the natural history and course of the disease being treated and any other disease the patient may have.
- Concomitant drug-
 - The other drugs the patient is taking or the treatment the patient receives should be examined to determine whether any of them might be recognized to cause the event in question.
- Known response pattern for this class of study drug-
 - Clinical and/or preclinical data may indicate whether a particular response is likely to be a class effect.
- Exposure to physical and/or mental stresses-
 - The exposure to stress might induce adverse changes in the recipient and provide a logical and better explanation for the event.

- The pharmacology and pharmacokinetics of the study drug-
 - The known pharmacologic properties (absorption, distribution, metabolism, and excretion) of the study drug should be considered.

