4.3 Withdrawal Criteria

Participation of a patient in this clinical study may be discontinued for any of the following reasons:

- The patient withdraws consent or requests discontinuation from the study for any reason;
- Occurrence of any medical condition or circumstance that exposes the patient to substantial risk and/or does not allow the patient to adhere to the requirements of the protocol;
- Any serious adverse event (SAE), clinically significant adverse event, severe laboratory abnormality, intercurrent illness, or other medical condition which indicates to the Investigator that continued participation is not in the best interest of the patient;
- Pregnancy;
- Requirement of prohibited concomitant medication;
- Patient failure to comply with protocol requirements or study-related procedures; or
- Termination of the study by the Sponsor or the regulatory authority.

If a patient withdraws prematurely from the study due to the above criteria or any other reason, study staff should make every effort to complete the full panel of assessments scheduled for the end of treatment visit (Week 12). The reason for patient withdrawal must be documented in the electronic Case Report Form (eCRF). In the case of patients lost to follow-up, attempts to contact the patient must be made and documented in the patient's medical records.

Withdrawn patients will not be replaced.

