9.13 Drug Induced Liver Injury Monitoring

With any of the following liver function test elevations, patients should undergo repeat laboratory measurements as soon as possible, preferably within 72 hours (unless otherwise specified), and no later than 1 week. Local laboratory measurements may be used to facilitate follow-up:

- ALT or AST $>8 \times$ ULN;
- ALT or AST $>3 \times$ ULN and bilirubin $>2 \times$ ULN or International Normalized Ratio $>1.5 \times$ ULN;
- ALT or AST $>3 \times$ ULN with the appearance of fatigue, nausea, vomiting, right upper quadrant pain or tenderness, fever rash, and/or eosinophilia ($>5\%$); and
- ALT or AST $>5 \times$ ULN, regardless of symptoms should be followed up within 1 week.

Repeat evaluation should include AST, ALT, prothrombin time/International Normalized Ratio, total bilirubin, alkaline phosphatase, gamma-glutamyltransferase, creatinine, CK, and complete viral hepatitis screen. The patient should be questioned regarding symptoms, as well as potential causative factors. This information, including results and normal ranges of any laboratory parameters collected at a local laboratory, should be collected on the appropriate eCRF. Hepatobiliary ultrasonography and/or consultation with a hepatologist should be considered if clinically indicated.

Abnormal laboratory parameters should be followed at least weekly (more frequently as clinically indicated) until they have returned to baseline or have stabilized.

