3.8.1 Adverse Events

Treatment-Emergent Adverse Events (TEAEs) are defined as adverse events that are new or worsen after the first dose of study drug. AE worsening applies to severity or relationship to study drug.

A summary overview of TEAEs will be provided, which presents the number and percentage of patients in each treatment group from the Safety Population satisfying each of the following categories:

- Any TEAEs,
- Maximum severity of TEAEs,
- Study drug-related TEAEs,
- Maximum severity of study drug-related TEAEs,
- All treatment-emergent serious adverse events (SAEs),
- All study drug-related TE-SAEs,
- TEAEs leading to death,
- TEAEs leading to study drug discontinuation, and
- Study drug-related TEAEs leading to study drug discontinuation.

Adverse events will be coded using MedDRA. The number and percentage of patients with TEAEs will be summarized by their MedDRA preferred term within system organ class and by treatment. AEs will be counted by the number of events as well as the number of patients. For event count summaries, multiple AE events with the same MedDRA coded terms (preferred term and system organ class) and onset date and time from the same patient will only be counted once. For patient count summaries, multiple AE events with the same MedDRA coded terms (preferred term and system organ class) from the same patient will only be counted once.

The number and percentage of patients with TEAEs will be summarized by reported maximum severity within each MedDRA preferred term within system organ class and by treatment.

The number and percentage of patients with TE-SAEs, any drug-related TEAEs, drug-related TE-SAEs, and TEAEs and TE-SAEs that lead to study drug discontinuation will be summarized by preferred term within system organ class and by treatment. In these summaries, any patients reporting multiple episodes of the same TEAE (i.e., same preferred term and system organ class) will be counted once.

All SAEs will be listed with an indication of whether the SAE was treatment emergent or started prior to treatment.

All TEAEs that are reported as leading to study drug discontinuation will be listed.

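### Adverse event severity is graded only by effect on daily life, so symptom-free liver-enzyme, CK and thyroid abnormalities fit *mild* at any size and the severity tables cannot rank them

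*Protocol*

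**What the plan says.** Protocol 9.1.3 applies one scale to all events: "The Investigator will assess the severity (intensity) of each adverse event as mild, moderate, or severe". The lowest level, *mild*, is "An event that is easily tolerated and generally not interfering with normal daily activities". The middle level asks for enough discomfort to get in the way of ordinary life. The top level is reached only by incapacity: "An event that is incapacitating with inability to work or perform normal daily activities".

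Protocol 9.1 requires these to be reported as adverse events: "Clinically significant abnormal laboratory or other examination (eg, ECG) findings that are detected during the study". The investigator judges clinical significance.

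The grade feeds planned output. Protocol 10.2.2 repeats the adverse event summary by severity. SAP 3.8.1 tabulates "Maximum severity of TEAEs", does the same for drug-related events, and breaks maximum severity down by preferred term.

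Two other sections treat laboratory values differently. Protocol 4.3 lists a "severe laboratory abnormality" among possible reasons for withdrawal. Protocol 9.13 says that ALT or AST above 5 times ULN "regardless of symptoms should be followed up within 1 week".

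**The concern.** Most laboratory abnormalities cause no symptoms, so a scale built on symptoms and function carries no information about their size. A symptom-free event cannot reach *moderate* or *severe*, however large the value. The safety profile, including thyroid hormone changes, is a secondary objective. The protocol also sets specific monitoring for liver enzymes (9.13) and TSH (3.1). A reader of the severity tables would naturally take *mild* to mean a small abnormality, which the definitions do not ensure. How much is lost depends on whether other planned tables show the size.

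**Working it through.** The plan states no figure to reproduce, so the check sets its rules side by side.

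**Step 1: apply 9.1.3 literally.** The values below are illustrative. Each is assumed to be symptom-free and judged clinically significant, so that it is reported.

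| Value | Grade as worded (Protocol 9.1.3) | Shift category (SAP 3.8.2.1) | Threshold count in the SAP |
|---|---|---|---|
| ALT 1.1 x ULN | mild | >ULN | none |
| ALT 3.1 x ULN | mild | >ULN | none |
| ALT 5.1 x ULN | mild | >ULN | none |
| ALT 8.1 x ULN | mild | >ULN | none |
| QTcF 455 msec | mild | not applicable | >450 |
| QTcF 485 msec | mild | not applicable | >450, >480 |
| QTcF 505 msec | mild | not applicable | >450, >480, >500 |

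The severity grade separates none of these values. The QTc thresholds separate the last three. No planned count separates the four ALT values.

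**Step 2: compare with Protocol 9.13.** Three of its four triggers can be met without symptoms: ALT/AST above 8 times ULN; above 3 times ULN with raised bilirubin or INR; and above 5 times ULN. An event can therefore call for prompt repeat testing and still fit *mild*.

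**Step 3: see what the other outputs recover.**

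- *Liver enzymes and CK.* SAP 3.8.2.1 gives visit statistics (SAP 3.1 includes the maximum), counts outside the normal range, and shifts to the worst value. Shift categories are below, within or above normal, with no multiples of ULN. Protocol 4.2 admits ALT up to 1.5 times ULN and CK up to 3 times ULN. A patient who enters above normal and then rises to 8 times ULN shows no shift.
- *Exclusion from the liver-enzyme analysis.* SAP 3.8.2.1 leaves out patients with possible liver disease, such as GGT above 100 U/L or direct bilirubin of at least 0.3 mg/dL. It states no time point, so an on-treatment rise could, read literally, remove the affected patient.
- *Thyroid.* Protocol Appendix B lists thyroid tests outside the chemistry and hematology panels, so SAP 3.8.2.1 does not reach them. SAP 3.8 names no thyroid summary, and SAP 3.8.6 only lists other safety data.
- *Abnormalities of special interest.* Protocol 10.2.2 promises a summary of these but does not define them, and SAP 3.8 does not take it up.
- *QTc.* SAP 3.8.3 counts values above 450, 480 and 500 msec and changes above 30 and 60 msec. Nothing is missing here.

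**The case against.** The strongest reply is that functional severity is only one descriptor. The investigator assigns the grade, and no passage says that a large symptom-free ALT must be called *mild*. Only clinically significant findings become adverse events. Those that do still appear by preferred term and arm, by relationship, and by discontinuation. They can also be serious as important medical events (Protocol 9.2). The triggers in 9.13 prompt repeat tests and are not grades. The phrase in 4.3 may be ordinary language in a discretionary criterion.

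Much of this stands, and it limits the point to ranking by size. It does not remove the point. An investigator who follows the three definitions has no basis for a higher grade, and one who departs from them does so without a common rule.

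A reader might go further in three ways that the documents do not support:

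- *The plan hides these harms altogether.* It does not. The events are tabulated, laboratory maxima are reported, and QTc is fully covered.
- *Table 1 of the protocol predicts how many patients are affected.* Its week 6 ALT data for eprotirome cover 5 + 14 + 3 + 2 = 24 and 4 + 11 + 3 + 3 + 1 = 22 patients, 46 in all. That is a different drug, and the protocol itself urges caution in the comparison. The highest band is 4 to 5 times ULN, so 0 of 46 exceeded 5 times ULN.
- *Raised transaminases are the chief liability of the class.* Protocol 1.1 lists several problems with earlier agents and does not rank them. It reports no liver-enzyme abnormalities in Phase 1 for MGL-3196 (1.1.1) and considers the TSH reduction that would trigger dose adjustment very improbable (1.2.3).

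**Conclusion.** The point holds as a gap in grading. On the wording of 9.1.3, symptom-free liver-enzyme, CK and thyroid abnormalities reported as adverse events fit *mild* whatever their size, so the maximum-severity tables cannot order them. For liver enzymes and CK the other outputs compensate in part. For thyroid tests SAP 3.8 names only the residual listing. QTc is outside the point.

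The effect is confined to descriptive safety tables; no endpoint, hypothesis test or sample size changes. The number of patients affected, and any distortion of the comparison between arms, cannot be estimated from the documents. The conclusion assumes that investigators apply the definitions as written and that no thyroid summary sits in the blacked-out text or in the separate table specifications. The correction is cheap and should be made.

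**What to change.** **Protocol 9.1.3.** Limit the daily-activity definitions to symptomatic events. Have laboratory adverse events graded from the measured value, with the mapping to the three grades written down before unblinding. If the event is also symptomatic, take the worse grade. The documents give no on-treatment grading cut-points for CK, so the mapping must name its source. State also how a symptom-free ECG finding is graded, so that the change leaves none ungraded.

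**SAP 3.8.2.** Add by-arm counts of patients whose worst post-baseline ALT or AST exceeds 3, 5 and 8 times ULN, which are the cut-points in Protocol 9.13. Add a count of patients who meet the TSH criterion in Protocol 3.1: below LLN, with a change of more than 50% from baseline, at two assessments in a row. Use the full Safety Population, so that the liver-disease exclusion does not apply to these counts.

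**Protocol 4.3.** Reconcile its reference to severe laboratory findings with the severity definitions.

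The cut-points serve reporting only, and patient management is unchanged. The counts use data already collected. The costs are a paragraph in the protocol, some SAP derivation, and linking adverse event terms to laboratory values, some of them from local laboratories. The severity table may also look slightly less favourable.
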